4.6.5 Safety Monitoring

Vital signs will be assessed immediately before and after injection of [⁶⁸Ga]DOTATATE (HR and supine BP). Patients will be monitored for adverse events during injection and after completion of the imaging study. Additionally, patient's vitals (HR and supine BP) will be checked at the completion of the imaging study prior to leaving the imaging center.

4.6.6 Patient Follow-Up

Patients will be instructed to contact the UAB Department of Radiology Advanced Imaging Facility if there are any concerns about delayed side effects related to the study radiotracer. Patients will be seen in the clinic if there are any concerning study related adverse events requiring further evaluation.

5.0 Study Parameters

5.1 Primary Endpoint

- Percentage of patients with moderate to high binding of [⁶⁸Ga]DOTATATE on PET examination
- Concordance between [⁶⁸Ga]DOTATATE PET results and liver MRI results

5.2 Study Termination

The study will stop enrolling patients once the target number has been reached.

6.0 Statistical Considerations

6.1 Study Design

This is a prospective pilot trial to determine the potential use of [⁶⁸Ga]DOTATATE PET for patients with hepatocellular carcinoma to assess feasibility of targeted radionuclide therapy with somatostatin receptor ligands. The primary objective of this study is to

determine if a sufficient fraction (20% or greater) of HCC seen on conventional anatomic imaging demonstrates levels of somatostatin receptor expression to result in a positive DOTATATE PET scan. If a sufficient fraction of patients demonstrate positive DOTATATE PET scans, this study could serve as the basis for a subsequent therapeutic clinical trial with [¹⁷⁷Lu]DOTATATE.

6.2 Sample Size Justification

As this is a pilot feasibility study, no formal hypothesis will be testing, and thus no power analysis was performed. The primary objective is to determine the frequency of somatostatin receptor positivity in hepatocellular carcinoma using [⁶⁸Ga]DOTATATE-PET. In this study, patients with treatment-naïve HCC (n=15) and patients with previously treated HCC being referred for systemic chemotherapy and/or best supportive care (n=15) will be enrolled through the UAB Hepatobiliary Tumor Board in order to estimate the percentage of patients with moderate to high binding of [⁶⁸Ga]DOTATATE on PET examinations. Patients will undergo a single whole body [⁶⁸Ga]DOTATATE-PET/MRI or PET/CT to assess SSTR positivity of their HCCs. If a sufficient fraction (20% or greater) of HCC seen on conventional anatomic imaging demonstrate levels of somatostatin receptor expression to result in a positive DOTATATE PET scan, a subsequent therapeutic clinical trial with [¹⁷⁷Lu]DOTATATE will be carried out. With a total of 30 patients enrolled, the estimated percentage of positive binding of [⁶⁸Ga]DOTATATE will have two-sided 95% confidence intervals (CI) from $7.7\% \leq p \leq 38.6\%$ using the Clopper-Pearson (exact) method assuming at least 20% positive binding occurs. Although the confidence interval will be wide for each subgroup, e.g. treatment-naïve HCC or previously treated HCC with n=15 (95% CI $4.3\% \leq p \leq 48.1\%$), it will provide early evidence if the [⁶⁸Ga]DOTATATE binding will be affected by prior treatment and/or stage of disease.

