2.0 Study Objectives

Specific Aim 1: Determine the frequency of somatostatin receptor positivity in hepatocellular carcinoma using [⁶⁸Ga]DOTATATE-PET

Hypothesis 1: [⁶⁸Ga]DOTATATE PET will be positive in at least 20% of patients with hepatocellular carcinoma (HCC).

Liver transplantation is the only curative therapy for HCC and is an option for a selected subset of HCC patients. For those who are not candidates for transplantation, locoregional therapies with limited efficacy are available such as percutaneous ablation,

arterial chemoembolization, and Y-90 microsphere radionuclide therapies. There are few options for patients who progress or are not candidates for these therapies. The first line systemic therapy is sorafenib, a tyrosine kinase inhibitor. Sorafenib is often not well tolerated due to its side effects and there is need for additional systemic treatments.

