3.3 Inclusion Criteria

- Known diagnosis of hepatocellular carcinoma, either by imaging criteria or pathology on biopsy
- Standard of care liver MRI or CT demonstrating viable HCC based on arterial contrast enhancement measuring at least 1.5 cm in largest axial dimension

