4.6.4 PET/CT and PET/MRI Imaging Interpretation and Storage

Images from the PET/CT and PET/MRI will be anonymized and subsequently stored and reviewed using a commercially available software package (MIM Encore, Cleveland, OH). The PET and whole body MRI studies will not be available in the UAB PACS system. This is in an effort to blind the treating physicians from making clinical decisions on an experimental imaging technique. The liver MRI images will be sent to clinical PACS and the medical record as part

of standard-of-care imaging and can be used in the clinical-decision making process. No formal interpretation will be generated for the [⁶⁸Ga]DOTATATE-PET or whole body MRI portion of the study.

PET/CT and PET/MRI images will be interpreted by board certified physicians specialized in molecular imaging and abdominal imaging. Images will initially be interpreted as positive or negative for SSTR-positive HCC. HCC lesions will be considered SSTR positive for the purposes of this study if they have higher [⁶⁸Ga]DOTATATE activity than adjacent liver not involved by HCC. The amount of [⁶⁸Ga]DOTATATE binding for intrahepatic HCCs will be further characterized based on visual analysis as less than skeletal muscle (no binding), higher than skeletal muscle but less than or equal to adjacent liver (low binding), higher than adjacent liver but less than spleen (moderate binding) or equal to or greater than spleen (high binding). For patients with SSTR-positive HCC and positive [⁶⁸Ga]DOTATATE PET, intrahepatic and extrahepatic disease will be assessed on MRI/CT alone first, with confidence in interpretation rated on a 1-5 scale (1 = negative, 5 definite). Following this, fused PET/CT or PET/MRI images will be assessed and rated on the same 1-5 scale.

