6.4 Statistical Analysis Plan

This study will largely be exploratory and descriptive. For all clinical and histological evaluations as well as imaging parameters, we will generate summary tabulations of the number of observations, mean, standard deviation, median, minimum, and maximum for continuous variables, and the frequency and percentage for categorical variables. Analyses will be primarily descriptive and graphical in nature. The count, and percentage of patients with HCCs showing activity in their HCC greater than liver and/or spleen will be estimated using Clopper-Pearson (exact) method along with two-sided 95% CI. The estimation will be provided for all 30 patients first, and then by treatment-naïve or not.

Concordance between [⁶⁸Ga]DOTATATE PET results and liver MRI results for patients with SSTR-positive HCC and positive [⁶⁸Ga]DOTATATE PET, intrahepatic and extrahepatic disease will be assessed on MRI/CT alone first, with confidence in interpretation rated on a 1-5 scale (1 = negative, 5 definite). Following this, fused PET/CT or PET/MRI images will be assessed and rated on the same 1-5 scale. Scale 3-4

is defined as positive. The agreement (concordance) between nominal (e.g. scale 1-5) or binary outcome (positive or negative) of [⁶⁸Ga]DOTATATE PET results and liver MRI results will be assessed using Cohen's kappa coefficients with one-side 95% confidence intervals. Based on values of Cohen's kappa, the agreement will be considered as poor (>0.2), fair (0.21-0.40), moderate (0.41-0.60), good (0.61-0.80), and very good (0.81-1.0) ([Dtsch Arztbl Int. Concordance Analysis. 2011 Jul; 108\(30\): 515-521. PMID: 21904584](#)). Bland-Altman diagrams will be used to evaluate agreement for other continuous imaging variables between these two methods. All statistical analysis will be carried on SAS v9.4.

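### Is the 20% criterion in 6.1 and 6.2 a fraction of lesions, at odds with an endpoint and confidence interval counted per patient?

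*Combined protocol and SAP*

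**What the plan says.** Section 6.1 gives the primary objective as to "determine if a sufficient fraction (20% or greater) of HCC seen on conventional anatomic imaging demonstrates levels" of receptor expression high enough for a positive scan. Its next sentence changes the noun: "If a sufficient fraction of patients demonstrate positive DOTATATE PET scans", the study could support a later therapeutic trial. Section 6.2 repeats the threshold ("If a sufficient fraction (20% or greater) of HCC seen on conventional anatomic imaging demonstrate levels of somatostatin receptor expression") and says more firmly that the therapeutic trial will then follow.

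Elsewhere the unit is the patient:

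- Hypothesis 1 (1.1 and 2.0): "PET will be positive in at least 20% of patients with hepatocellular carcinoma (HCC").
- Primary endpoint (5.1): "Percentage of patients with moderate to high binding of" the tracer.
- Planned estimate (6.4): "percentage of patients with HCCs showing activity in their HCC greater than liver and/or spleen", with a Clopper-Pearson interval.
- Precision statement (6.2): two-sided 95% limits of 7.7% to 38.6% for 30 patients, and 4.3% to 48.1% for each subgroup of 15.

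Positivity itself is defined on lesions in 4.6.4: "HCC lesions will be considered SSTR positive for the purposes of this study if they have higher" activity than adjacent uninvolved liver. Entry under 3.3 needs viable HCC "measuring at least 1.5 cm in largest axial dimension" and sets no limit on the number of lesions.

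**The concern.** Taken alone, the threshold clause describes tumours visible on CT or MRI, so its denominator could be lesions. Because 4.6.4 scores lesions and 3.3 admits patients with several, the two denominators can differ. The go criterion and the primary endpoint could then fall on opposite sides of 20% in the same data. The interval in 6.2 assumes one independent result per patient and would not describe a lesion fraction.

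A second worry follows. If the unit is the patient, a rule is needed for patients whose lesions disagree: any lesion, all lesions, or one index lesion. None is written out, so in principle it could be picked after the images are read, when the choice might decide whether 20% is reached.

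**Working it through.** **1. Reproduce the plan's figure.** Inputs from 6.2: n = 30, rate 20%, so x = 0.20 × 30 = 6. For each subgroup n = 15 and x = 0.20 × 15 = 3. Clopper-Pearson limits are the 2.5% quantile of Beta(x, n − x + 1) and the 97.5% quantile of Beta(x + 1, n − x).

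| x/n | Lower | Upper | Stated in 6.2 |
|---|---|---|---|
| 6/30 | 7.71% | 38.57% | 7.7% to 38.6% |
| 3/15 | 4.33% | 48.09% | 4.3% to 48.1% |

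Both match with patients as the denominator.

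**2. Read the threshold clause to its end.** In 6.1 and 6.2 the clause finishes by requiring expression sufficient for a positive DOTATATE PET scan. Under 1.1 and 6.2 each patient has a single scan, so a positive scan is a patient-level event. Where the protocol means individual tumours, as in 4.6.4, it says lesions. In 6.2 the sentences around the threshold speak of the percentage of patients and of 30 patients enrolled.

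**3. Look for a lesion-level analysis.** There is none. No section plans a lesion count as a denominator or an estimate of a lesion fraction.

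**4. Derive the patient result.** Section 4.6.4 first has the images read as positive or negative for SSTR-positive HCC. That is a question of presence, so one positive lesion suffices; the wording of 6.4 points the same way. On the ordered scale of 4.6.4, moderate binding starts above adjacent liver and high binding starts at spleen level, so moderate or high together means above adjacent liver. That is also the cut for SSTR-positive. The binary scan read therefore gives the 5.1 endpoint for intrahepatic disease without a separate patient-level grade.

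**5. Size of a conflict, if lesions were the unit.** The documents give no lesion counts, so these are constructed cases.

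- 15 patients with one lesion and 15 with two (45 lesions), six patients with one positive lesion each: 6/30 = 20.0% against 6/45 = 13.3%.
- 25 patients with one negative lesion and five with two positive lesions (35 lesions): 5/30 = 16.7% against 10/35 = 28.6%.

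**6. Size under a model.** Let lesion positivity be p, lesions per patient m and within-patient correlation ρ (beta-binomial with a = p(1/ρ − 1), b = (1 − p)(1/ρ − 1)). At ρ = 0 the any-lesion rate is 1 − (1 − p)^m.

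- p = 10%, m = 3: 1 − 0.9³ = 27.1% at ρ = 0, 21.7% at ρ = 0.25, 10.0% at ρ = 1. The gap to the lesion rate runs from 17.1 points to 0.
- p = 10%, m = 2: at most 1 − 0.9² = 19.0%, so both units stay below 20%.
- p = 20%, m = 2 or 3, ρ from 0 to 0.8: 23% to 49%, so the expected lesion and patient rates both reach 20%.
- m = 1: no gap.

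**The case for a change.** The strongest opposing case concerns the unwritten multi-lesion rule. Section 6.2 commits to a therapeutic trial if 20% is met, and a stated go criterion deserves a defined numerator even without a test. In the model with p = 20%, two or three lesions and ρ from 0 to 0.8, the chance of at least 6 positive patients in 30 is 73% to over 99% if any positive lesion counts. It is under 1% to 39% if all lesions must be positive, and 57% with one lesion per patient. The rule can matter.

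What stands is that the any-lesion rule is implied and not spelled out, and that the threshold clause is loosely worded. What does not stand is that the choice is open. Nothing in the documents suggests an all-lesion or index-lesion rule, while the scan-level read in 4.6.4 and the wording of 6.4 both favour any positive lesion. An index-lesion rule would be a different trade-off, not a correction: with p = 10% and three lesions it gives 10.0%, where the any-lesion rule gives 10.0% to 27.1%.

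The consequences are also softer than 6.2 alone suggests. Section 6.1 says only that the study could serve as a basis for a later trial, and 1.1 that a positive result would justify future studies. Section 6.2 rules out formal testing, and an interval of 7.7% to 38.6% makes 20% a planning mark.

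**Conclusion.** The concern does not call for a change. The threshold clause is ambiguous in isolation, but its own ending, the next sentence of 6.1, Hypothesis 1, 5.1, 6.4 and the interval in 6.2 all make the patient the unit. Putting patients in place of HCC would leave the 6-of-30 mark, the estimate and the limits as they are. The multi-lesion rule is a detail that analysts following 4.6.4 and 6.4 would fill sensibly: a patient is positive if at least one lesion exceeds adjacent liver.

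The effect on the planned analysis is nil under that reading. The gaps of up to 17.1 points arise only if lesions are taken as the unit, and they rest on assumed lesion counts, a 10% lesion positivity and assumed correlations. The only range the protocol cites is 20-50% of HCCs positive in tissue studies (1.2). Tissue is not PET, so this is only a loose guide, but at 20% or more, with equal lesion counts, the expected per-lesion and any-lesion rates both reach the mark. The conclusion assumes that the scan-level read is applied as 4.6.4 describes.

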1.0 Introduction and Study Rationale

1.1 Overview

There is great need for new therapeutic options for patients with hepatocellular carcinoma (HCC). This study will assess the feasibility of a novel theranostic approach to hepatocellular carcinoma (HCC) using [⁶⁸Ga]DOTATATE, a recently FDA-approved positron emission tomography (PET) ligand for imaging somatostatin receptor (SSTR) positive tumors. This PET tracer is in routine clinical use for neuroendocrine tumors (NET) but to our knowledge has not been systematically applied to HCC. The objective of this study is to measure the frequency of SSTR positivity in hepatocellular carcinoma using [⁶⁸Ga]DOTATATE-PET. We hypothesize that [⁶⁸Ga]DOTATATE-PET will be positive in at least 20% of patients with HCC. If this current study shows a substantial fraction HCCs have moderate to high SSTR levels based on PET imaging, this result would justify future studies evaluating targeted radionuclide therapy (TRT) with the therapeutic SSTR ligand [¹⁷⁷Lu]DOTATATE which was recently FDA approved for treating SSTR-positive NETs arising from the gastrointestinal tract.

Study objective: Determine the frequency of somatostatin receptor positivity in hepatocellular carcinoma using [⁶⁸Ga]DOTATATE-PET

Hypothesis: [⁶⁸Ga]DOTATATE PET will be positive in at least 20% of patients with hepatocellular carcinoma (HCC).

In this study, patients with treatment-naïve HCC (n=15) and patients with previously treated HCC being referred for systemic chemotherapy and/or best supportive care (n=15) will be enrolled. Patients will undergo a single whole body [⁶⁸Ga]DOTATATE-PET/MRI to assess SSTR positivity of their HCCs. The percentage of patients with HCCs showing activity in their HCC greater than liver and/or spleen will be calculated.

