[⁶⁸Ga]DOTATATE (tradename NETSPOT) is a peptide-based radiopharmaceutical for positron emission tomography (PET) that was approved for clinical use in the United States in 2016 for the evaluation of somatostatin receptor (SSTR)-positive neuroendocrine tumors (NETs). This PET tracer binds to SSTRs on the surface of tumor cells with the highest affinity for the SSTR2 receptor which is overexpressed in neuroendocrine tumors. In patients with metastatic NETs, somatostatin analogues (e.g. octreotide and lantreotide) are a mainstay in control of symptoms, but do not treat the underlying metastatic disease. In 2018, the FDA approved a therapeutic analogue of DOTATATE ([¹⁷⁷Lu]DOTATATE, tradename Lutathera) for the treatment of SSTR-positive gastroenteropancreatic NETs. A key concept is that [⁶⁸Ga]DOTATATE-PET is used to evaluate metastatic NETs for SSTR expression and use this information to select potential candidates for [¹⁷⁷Lu]DOTATATE therapy. This theranostic approach can potentially be applied to other tumors that express adequate levels of SSTR.

SSTR expression has previously been demonstrated in the setting of HCC to varying degrees. A study of 53 resected HCCs demonstrated that membrane SSTR2 was reliably detected in HCC and could serve as a potential therapeutic target.[4] Multiple tissue-based studies demonstrate SSTR positivity in 20-50% of HCCs.[4-6] Additionally, SSTR2 expression in HCC was positively correlated with cytokeratin 19-9 expression, serum alpha-fetoprotein level, and poor differentiation, all of which are poor prognostic markers for patients with HCC.[4, 7, 8] Additional studies have confirmed SSTR expression in HCC with varying distributions of the SSTR receptor subtype expression.[5, 6] However, the fraction of HCCs have high enough levels of SSTR for [¹⁷⁷Lu]DOTATATE therapy has not yet been assessed. Therefore, it is our aim to use [⁶⁸Ga]DOTATATE-PET/MRI to assess tumor SSTR expression in patients with HCC before and after locoregional therapy. This research plan is a critical prerequisite for determining the feasibility of this theranostic approach to treating HCC. If we obtain positive results, these data will be critical for designing a combined imaging and therapeutic study in HCC using DOTATATE.

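### Does tying the 7.7–38.6% interval to a rate of at least 20%, and leaving the reading of that 20% unstated, call for a change to Section 6.2?

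*Combined protocol and SAP*

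**What the plan says.** Section 6.2 declares that "no formal hypothesis will be testing, and thus no power analysis was performed" and justifies 30 patients by precision alone. It gives an exact two-sided 95% interval of 7.7% to 38.6%, "using the Clopper-Pearson (exact) method assuming at least 20% positive binding occurs". For each group of 15 it gives 4.3% to 48.1%, calls that interval wide, and prints no separate condition beside it.

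The 20% figure first appears in the hypothesis of Section 2.0, that "PET will be positive in at least 20% of patients with hepatocellular carcinoma". Section 6.2 uses it as a trigger: "If a sufficient fraction (20% or greater) of HCC seen on conventional anatomic imaging demonstrate levels of somatostatin receptor expression" high enough for a positive scan, then a trial of lutetium-177 "DOTATATE will be carried out". Section 6.1 is more cautious about the same event: "this study could serve as the basis for a subsequent therapeutic clinical trial". Section 1.1 is closer to 6.1, saying of a substantial positive fraction that "this result would justify future studies evaluating targeted radionuclide therapy".

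Section 6.4 plans a count, a percentage and a Clopper-Pearson 95% interval, for all patients and then by prior treatment. It does not mention 20%.

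**The concern.** Three things catch the eye.

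- **The condition on the interval.** Clopper-Pearson limits are a function of the observed count. A single pair of limits cannot describe every result from 20% upwards. The background in Section 1.2 states that "Multiple tissue-based studies demonstrate SSTR positivity in 20-50% of HCCs". Tissue positivity is not PET positivity, but if PET behaved similarly the count would lie between 6 and 15 of 30, and the printed interval is the narrowest over that range. The design could look more precise than it is.
- **The meaning of reaching 20%.** The primary objective in 6.1 turns on this threshold, yet no section says what is compared with it. Six positives suffice if it is the observed percentage. Twelve would be needed if the lower 95% limit had to reach 20%. A reader told that 20% was met at 6/30 might wrongly take the Section 2.0 hypothesis as established.
- **The consequence.** Section 6.2 reads as a commitment to a therapeutic trial, while 6.1 and 1.1 read as permission for one.

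If these points affected the analysis or the conclusions, they would need settling before data are seen.

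**Working it through.** **Inputs.** n = 30 in total and 15 per group; two-sided 95%; Clopper-Pearson; planning rate 20% (all from Section 6.2). Plausible range 20% to 50% (Section 1.2, tissue studies).

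**Step 1: reproduce the plan's figures.** For x positives of n, the lower limit is the 0.025 quantile of Beta(x, n − x + 1) and the upper limit is the 0.975 quantile of Beta(x + 1, n − x).

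- 0.20 × 30 = 6. Beta(6, 25) gives 7.71% and Beta(7, 24) gives 38.57%. The plan prints 7.7% and 38.6%.
- 0.20 × 15 = 3. Beta(3, 13) gives 4.33% and Beta(4, 12) gives 48.09%. The plan prints 4.3% and 48.1%.

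Both reproduce. Wald, Wilson, Agresti-Coull and Jeffreys intervals at 6/30 do not give the printed limits, so the method is also as stated.

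**Step 2: see how far the condition misleads.** The background range corresponds to 0.20 × 30 = 6 up to 0.50 × 30 = 15 positives. Widths come from unrounded limits; the last column is (width − 30.85)/2.

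| Positives of 30 | Observed % | 95% limits (%) | Width (points) | Extra half-width |
|---|---|---|---|---|
| 6 | 20.0 | 7.71 to 38.57 | 30.85 | 0 |
| 7 | 23.3 | 9.93 to 42.28 | 32.35 | 0.75 |
| 9 | 30.0 | 14.73 to 49.40 | 34.66 | 1.90 |
| 12 | 40.0 | 22.66 to 59.40 | 36.74 | 2.94 |
| 15 | 50.0 | 31.30 to 68.70 | 37.41 | 3.28 |

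By symmetry the excess falls back to 0.75 at 23/30 and to 0 at 24/30. The lower limit rises with the count, so 7.7% is a valid floor for every result of 6 or more. The wording fails for the upper limit and, from 7 to 23 positives, for the width.

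**Step 3: ask what uses the printed interval.** Section 6.2 states no maximum width and no power, so the wider intervals miss no target. Section 6.4 recomputes the limits from the observed count: with 9 positives the report will give 14.7% to 49.4%, whatever 6.2 says.

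**Step 4: read the 20% threshold in context.** Section 6.2 speaks of a fraction and rules out a formal test; Section 6.4 describes a mostly descriptive analysis. No section compares a confidence limit with 20%. The lower-limit reading would need 12/30, since 11/30 has a lower limit of 19.93% and 12/30 has 22.66%. If the true rate were 40% (an illustrative assumption), P(X ≥ 12) for Binomial(30, 0.40) is 0.569. A rule missed more than four times in ten at twice the hypothesised rate is unlikely to be what a 30-patient pilot intended. The observed-fraction reading, 6 or more of 30, is the natural one.

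**Step 5: set the consequences side by side.** Sections 1.1, 6.1 and 6.2 all speak of a separate later study. Neither the firm nor the permissive wording alters enrolment, scanning, analysis or reporting here.

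**The case for a change.** The best argument for amending is that the wording is wrong on its face and cheap to correct. Over the counts that the plan's own background makes plausible, the printed interval is the most favourable one, so the phrase cannot be defended as a worst case for precision. Section 6.2 also attaches a follow-on trial to a threshold without saying how it is judged. If the observed fraction is meant, the threshold will sometimes be met when the true rate is lower: at an assumed true rate of 15%, P(X ≥ 6) for Binomial(30, 0.15) is 0.289. One added sentence would guard against over-reading.

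Much of this is true. The condition is inaccurate, and 6.1 and 6.2 do not match. What does not follow is that the plan would produce anything unsound. The caution that meeting 20% does not establish a true rate of 20% is already visible in 6.2, because the lower limit printed for exactly that result is 7.7%. Section 6.4 requires the interval to be reported with the percentage, so whoever decides on a later trial will see that uncertainty. The alternative reading of the threshold has no support in the text.

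**Conclusion.** No change to the plan is needed. The limits in Section 6.2 are correctly computed at 6/30 and 3/15; the condition attached to the first is a clerical slip that understates the half-width by at most 3.3 points (15.4 against 18.7). The reading of 20% is a gap with one natural filling, the observed fraction. The difference between 6.1 and 6.2 is editorial and concerns a trial that this protocol does not govern. Sample size, analysis and reported results would be the same under corrected wording.

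This rests on three things: that Section 6.4 is followed, so that the interval comes from the observed count; that no precision target exists beyond what 6.2 prints; and that 20% remains a feasibility guide, as the absence of a formal test implies. The 20% to 50% range comes from tissue studies and serves only to show which counts are plausible; the true rates of 15% and 40% are illustrative.

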3.0 Investigational Plan

3.1 Study Design

The project will be a pilot prospective IRB-approved HIPAA-compliant study that will enroll 15 patients with untreated HCC and 15 patients with previously treated HCC. These patients will be identified at weekly multidisciplinary hepatobiliary conference in collaboration with liver transplant surgery, interventional radiology, diagnostic radiology, hematology/oncology, gastroenterology, and radiation oncology. Patients will undergo standard-of-care treatment based on recommendations of hepatobiliary tumor board. The preferred imaging modality will be PET/MRI, owing to its superior soft tissue characterization of the liver and abdominal soft tissues when compared to non-contrast CT performed for PET/CT. However, understanding that patients may have large volume ascites or claustrophobia, PET/CT may be utilized as an alternative in select patients at the discretion of the Principal Investigator. The study will be performed within 4 weeks of most recent conventional anatomic imaging with either CT or MRI to minimize the potential to alter clinical management on the basis of the CT or MRI portion of the research examination.

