3.2 Study Population

- Patients with treatment naïve hepatocellular carcinoma and patients with previously treated hepatocellular carcinoma being referred for systemic chemotherapy and/or best supportive care

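### The two groups of 15 are offered as early evidence on prior treatment and/or stage, but the planned separate intervals do not estimate a difference and could not attribute one to either factor

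*Combined protocol and SAP*

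**What the plan says.** Section 3.1 will "enroll 15 patients with untreated HCC and 15 patients with previously treated HCC". Section 3.2 describes the second group more narrowly, as patients with "previously treated hepatocellular carcinoma being referred for systemic chemotherapy and/or best supportive care". Section 6.2 uses that narrower description too. It prints the count of 15 after each group separately, which ties the referral condition to the second group.

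Section 6.2 gives a 95% interval of 7.7% to 38.6% for all 30 patients, "using the Clopper-Pearson (exact) method assuming at least 20% positive binding occurs", and 4.3% to 48.1% for a group of 15. It concedes that the subgroup intervals are wide. It then says that they will nevertheless give early evidence on whether "binding will be affected by prior treatment and/or stage of disease". The same section states that there is no formal hypothesis test and no power analysis.

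Section 6.4 sets out the matching output: "The estimation will be provided for all 30 patients first", followed by the same estimate split by whether patients were treatment-naïve. It lists no between-group difference, no interval for one and no estimate of positivity by stage. The inclusion and exclusion criteria (sections 3.3 and 3.4) do not mention stage.

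**The concern.** Whether binding is affected by a factor is a question about a contrast. To answer it, an analysis has to estimate the contrast, and the design has to let the contrast be read as the effect of that factor. Neither holds here.

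The single split carries two things at once: having been treated, and having reached referral for systemic or supportive care. The groups are not randomised, and each patient is scanned once.

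What is at stake is how the subgroup results are read. Two wide intervals side by side, under a protocol that promises evidence of an effect, invite one of two errors. A gap of a few patients may be reported as an effect of treatment or stage, or overlapping intervals may be reported as showing no effect.

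**Working it through.** **1. What the grouping can identify.** Set prior treatment against point in care, using sections 3.2 to 3.4 and 6.2:

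| | Referred for systemic or supportive care | Not so referred |
|---|---|---|
| Previously treated | 15 patients | none, by the group definition |
| Treatment-naïve | not restricted | not restricted |

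Write *a* and *b* for the unknown fractions with advanced disease in the naïve and treated groups, and *p_A* and *p_E* for positivity in advanced and earlier disease. If prior treatment had no effect at all, the expected difference (treated minus naïve) would still be (*b* − *a*)(*p_A* − *p_E*). The documents give none of these four quantities, and section 6.4 plans nothing that would estimate them. Section 1.2 does make *p_A* ≠ *p_E* plausible: it reports that SSTR2 expression correlates with markers of poor prognosis. A difference in the results could therefore be due to treatment, to stage or to both, and the planned output would not tell them apart.

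**2. The plan's own intervals.** Clopper-Pearson limits for *x* of *n* are the 2.5% quantile of Beta(*x*, *n* − *x* + 1) and the 97.5% quantile of Beta(*x* + 1, *n* − *x*).
- 6/30: 7.71% to 38.57% (plan: 7.7% to 38.6%).
- 3/15: 4.33% to 48.09% (plan: 4.3% to 48.1%).

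Both reproduce. Both are one-sample intervals.

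**3. The interval for the difference.** Inputs: 15 per group and 20% positivity (section 6.2), two-sided 95% (section 6.4). The other counts below are assumptions, because the documents give no between-group rates.

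Wilson limits are [*p* + z²/2n ± z√(*p*(1 − *p*)/n + z²/4n²)] / (1 + z²/n), with z = 1.96 and n = 15:
- 3/15: 7.05% to 45.19%
- 6/15: 19.82% to 64.25%
- 10/15: 41.71% to 84.82%

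Newcombe limits for *d* = *p*₁ − *p*₂ are *d* − √[(*p*₁ − *l*₁)² + (*u*₂ − *p*₂)²] and *d* + √[(*u*₁ − *p*₁)² + (*p*₂ − *l*₂)²].
- 3/15 against 3/15: 0 ± √(0.1295² + 0.2519²) = ±0.283, so −28.3 to +28.3 points.
- 6/15 against 3/15: 0.200 − √(0.2018² + 0.2519²) = −0.123, and 0.200 + √(0.2425² + 0.1295²) = 0.475, so −12.3 to +47.5 points.
- 10/15 against 3/15: 0.467 − √(0.2495² + 0.2519²) = 0.112, and 0.467 + √(0.1816² + 0.1295²) = 0.690, so +11.2 to +69.0 points.

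**4. Why side-by-side intervals are a poor substitute.** In the last case the Clopper-Pearson intervals are 38.4% to 88.2% and 4.3% to 48.1%. They overlap, yet the interval for the difference excludes zero, so overlap cannot be read as no difference. In the other direction, suppose both true rates are 20%. The chance that the counts differ by 3 or more patients (20 points or more) is the sum of Bin(*i*; 15, 0.2) × Bin(*j*; 15, 0.2) over |*i* − *j*| ≥ 3, which is 0.249. At 30% in both groups it is 0.318. The 3-patient gap is an illustration; the protocol attaches no rule to it.

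**The case against.** The protocol is candid. It claims early evidence rather than proof, prints the wide subgroup interval, plans no test and calls the study largely exploratory and descriptive. The words and/or can be read as saying that a difference might reflect either factor or both. A reader can also derive the difference from the two reported counts. All of this stands, and it lowers the severity. It does not repair the inference: admitting imprecision does not separate the two factors, and larger groups defined in the same way would not separate them either. The general tabulation of clinical variables in section 6.4 does not relate stage to binding.

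Four stronger readings are tempting, and the documents do not support them.
- **The comparison is underpowered.** No test is planned and no between-group effect is specified, so power is not a standard this pilot sets itself, and its absence is no fault.
- **Treatment and stage are wholly aligned by design.** Stage is not restricted in either group, and a treatment-naïve patient may have advanced disease. The confounding is likely, but it is not shown to be complete.
- **A misreading would misdirect the therapeutic trial.** The criterion in sections 6.1 and 6.2 is an overall fraction of 20% or greater. No subgroup result enters it.
- **Section 1.2 promises a paired comparison.** Its aim "to assess tumor SSTR expression in patients with HCC before and after locoregional therapy" is background wording that can be read across patients. Sections 1.1 and 6.2 are explicit that each patient has a single scan, and no paired analysis is planned.

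**Conclusion.** The point holds in a limited form, with low severity. The analysis in section 6.4 yields two one-sample intervals. It does not estimate a difference in positivity, and it could not attribute one to prior treatment or to stage. The clause in section 6.2 therefore claims more than the planned output can give.

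If both groups are at 20%, the uncertainty on the difference is about 28 points either way. That figure rests on 15 evaluable patients per group and on the protocol's 20%; other rates would change it. The attribution problem rests on the group definitions and the lack of any analysis by stage, and does not depend on these numbers. The primary estimate, the sample size and the overall 20% criterion are unaffected.

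**What to change.** In section 6.2, replace the clause on prior treatment and stage with: *Group results are descriptive; the groups are likely to differ in both prior treatment and stage, so a difference will not be attributed to either.* State there the expected half-width of the 95% interval for the difference, about 28 points if both groups are at 20%.

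In section 6.4, add the between-group difference in positivity with a two-sided Newcombe 95% interval, next to the two group estimates.

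The cost is one line of output and a more modest stated aim. Enrolment, imaging and the primary analysis do not change.
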